#### 9.4.3 Handling of missing values/censoring/discontinuations

#### Part 1 (PK/PD)

All concentrations below the lowest limit of quantitation (LLOQ) or missing data will be labeled as such in the concentration data listings. Concentrations below the LLOQ will be treated as zero in summary statistics and for the calculation of PK parameters.

The statistical analysis will include all subjects with valid PK parameters.

#### Part 2 (Efficacy)

All efforts should be made to collect all information including vital status for all patients at the 52 week visit, or the last on-treatment assessment visit for the USM impacted patients.

For the primary efficacy endpoint, missing information will be handled as follows.

Patients will be classified into the worst possible category, based on available and retrievable information for the patient. Within Categories 1 and 2, patients will be further ranked according to the day of the last reliable information (for example, last day of contact). If the patient is not classified as Categories 1 or 2 (e.g. patient is alive and is documented to not have any WHF events), the same principle will be followed for ranking the patient.

If the 52 weeks measurements, or the last on-treatment assessment visit for the USM impacted patients, of NYHA classification or Ross classification and the PGIS score are missing then the last-observation-carried-forward (LOCF) technique will be used to impute the missing post-randomization values (for patients who do not experience any events in Category 1 or 2). Only post-randomization values will be used for imputation.

Page 117

Categories 3, 4, and 5 will be determined based on available information if the NYHA/Ross. PGIS, and PedsQL physical functioning domain are not complete. When ranking these patients, the ranking algorithm will place the patients at the median for the missing assessment component(s).

#### 9.4.4 Sensitivity analyses

In addition to the primary analysis, the primary efficacy endpoint will also be analyzed using the same primary analysis model in the PP population.

For the USM-impacted patients, the full data, including the off-treatment part, from the impacted patients will be included as a sensitivity analysis.

#### 9.4.5 Supportive analyses

To characterize the treatment difference between LCZ696 compared to enalapril, an ordered categorical endpoint with 5 categories, as used for deriving the primary endpoint variables, will be analyzed using a stratified Wilcoxon rank-sum test. The number and percent of patients within each individual category will be summarized by treatment group.

#### 9.5 Analysis of secondary variables

#### 9.5.1 Efficacy variables

#### Part 1 (PK/PD)

The objective of this part is to characterize the PK and PD of LCZ696 in pediatric patients with HF. Primary variables are described in Section 9.4.1. There are no specific secondary variables in Part 1.

#### Part 2 (Efficacy)

To determine whether LCZ696 is superior to enalapril, Part 2 (Efficacy) variables include

- Time to first Category 1 or 2 event
- Change from baseline (randomization visit) for NYHA/Ross class
- Change from baseline (randomization visit) for PGIS
- Population PK of LCZ696 exposure in pediatric patients with HF, including an assessment of steady-state sparse PK data in a subset of Group 2 patients, to further confirm the LCZ696 target dose for Group 2.

The full analysis set will be used in analyses for secondary endpoints.

With the same reasons described for the primary analysis, for the USM-impacted patients, the relevant assessments at the time of treatment discontinuation will be utilized in the secondary analyses (on-treatment approach).

For the USM-impacted patients, the full data, including the off-treatment part, from the impacted patients will be included as the sensitivity analyses.

The time to event endpoints will be analyzed using Cox's proportional hazards model with treatment as fixed-effect factor stratified by modified age group (Group 1: 6 to < 18 years; Group 2a: 2 to < 6 years; Group 3a: 1 month to < 2 years). The estimated hazards ratio and the corresponding two-sided confidence interval will be provided.

NYHA/Ross class and PGIS will be compared for LCZ696 and enalapril at week 52, respectively. Change from baseline at week 52 for these assessments will be analyzed based on a proportional cumulative odds model, stratified by modified age group (Group 1: 6 to < 18 years; Group 2a: 2 to < 6 years; Group 3a: 1 month to < 2 years) in which treatment will be included as fixed-effect factors and baseline value as a covariate. The treatment comparison between LCZ696 and enalapril for the secondary objective is to be made at week 52. This model assumes that the treatment effect sizes across measurement categories are the same. The effect size estimates and their 95% confidence intervals will also be provided.

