#### **Amendment rationale**

An urgent safety measure (USM) has been implemented, effective 26 October 2021, in consideration of a quality event affecting the active comparator (Enalapril) used in this study in order to maintain the safety of the patients and the integrity of this ongoing study.

Recruitment closed in January 2021 and 339 of 375 randomized patients who received study drug, have completed or were discontinued from the study at the time the USM was issued. The study is expected to be completed by early January 2022. Thirty-six (36) patients were ongoing as of 26 October 2021, of whom 5 had discontinued study medication. Thirty-one (31) patients were taking study medication at the start of the USM. As of 31 October 2021, all patients had to discontinue study drug treatment and be changed to local standard of care, respecting required washout periods. The changes included in this amendment in the context of the USM are intended to maintain the scientific integrity of the study.

This amendment is to reflect the action taken under the USM and revise the primary analysis to account for the USM.

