#### Amendment rationale

The main reasons for this amendment are as follows:

- Based on review of Part 1 Age Group 3 PK/PD/Safety data, this amendment defines the target dose and dose regimen for Part 2 Age Group 3 to enable enrollment into Part 2 for Age Group 3. The planned target dose of LCZ696 2.3 mg/kg bid for Part 2 Age Group 3 together with the implementation of additional hypotension safety monitoring for Part 2 Age Group 3 during the initial up-titration phase is supported by the DMC and has been added to the protocol with this amendment. The DMC also supports the protocol changes with this amendment that enables Age Group 3 patients who turn 1 year old during Part 2 of the study and who are safely tolerating the LCZ696/placebo 2.3 mg/kg bid dose, to be able to up-titrate to LCZ696/placebo 3.1 mg/kg bid dose (the target dose for Age Group 2), if it is in the patient's best interest as assessed by the Investigator.
- Based upon agreement with the EMA/PDCO (PIP M04) to align the age groups with the ICH E11 guidelines on pediatric subsets, modified age groups that will be included in the analysis.
- The enrollment target of 25% ACEI/ARB naïve patients has been removed, as it is considered not attainable given that patients in this study population are often initially treated with some form of RAS inhibition when first diagnosed. Ninety percent (90%) of the patients have been randomized thus far and only a small percentage (approximately 5%) of these patients are ACEI/ARB naïve.
- The requirement to include 20% randomized patients per age group in the analysis of Part 2 has been removed. Given the challenges of recruiting patients 1 month to <1 year old (Age Group 3), it is considered not feasible to enroll 72 patients (20% of 360 patients) in this age group. The requirement for 80 patients with an event in Category 1 or 2 has also been removed. The study is sufficiently powered based on the Global Rank Endpoint and the number of patients expected to have a Category 1 or 2 event.
- Patients in Age Group 2 will be required to be Ross class II or higher at randomization. This is based on the lower event rate observed in Age Group 2 patients vs. Age Group 1 patients.
- Measurement of height has been clarified with a statement recommending use of a stadiometer for standing height measurements.

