#### 4 **Population**

The study population consists of pediatric HF patients 1 month to < 18 years, inpatient or outpatient, with systemic left ventricle systolic dysfunction (LVEF ≤45% or a fractional shortening  $\leq 22.5\%$ ). For inclusion criteria details regarding LVEF and fractional shortening, refer to Section 4.1. The study will enroll at least 18 patients in Part 1 and 360 patients in Part 2 (Efficacy) at centers worldwide. With an expected screen failure rate of 35% for both Part 1 (PK/PD) and Part 2 (Efficacy), it is estimated that approximately 46 patients will have to be screened for Part 1 and 554 patients will have to be screened for Part 2.

For Part 1, at least 18 subjects will be divided across three groups based on age: **Group 1**: 6 to < 18 years (6 observations for the LCZ696 0.8 mg/kg dose and 6 observations for the LCZ696 3.1 mg/kg dose); Group 2: 1 to < 6 years (6 observations for the LCZ696 0.8 mg/kg dose and 6 observations for the LCZ696 3.1 mg/kg dose); **Group 3**: 1 month to < 1 year (approximately 4 observations for LCZ696 -0.4 mg/kg dose and approximately 4 observations for the LCZ696 1.6 mg/kg dose). Eligible patients will participate in the LCZ696 0.8 mg/kg and 3.1 mg/kg doses in Groups 1 and 2 and in the LCZ696 0.4 mg/kg and 1.6 mg/kg doses in Group 3. Patients who do not participate in the LCZ696 3.1 mg/kg (Group 1 or 2) or 1.6 mg/kg (Group 3) dose will be replaced. To ensure that patients are enrolled in both high and low end of the 6 to < 18 years of age group, approximately 50% patients will be enrolled who are 6 to 11 years of age in Group 1.

For Part 2, patients will be stratified by age (Age Groups 1, 2 and 3) and NYHA/Ross class group (Class I/II, Class III/IV) at randomization to ensure a balanced distribution of treatment allocation within each age group. Patients who discontinue from Part 2 will not be replaced.

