# 5.3 Treatment assignment and randomization

At Visit 401, all eligible patients will be randomized via Interactive Response Technology (IRT) to one of the treatment arms. Patients will be stratified by age group (Age Groups 1, 2 and 3) and NYHA/Ross class group (Class I/II, Class III/IV) at randomization to ensure a balanced distribution of treatment allocation within each age strata. The Investigator or his/her delegate will contact the IRT after confirming that the patient fulfills all the inclusion/exclusion criteria. The IRT will assign a randomization number to the patient, which will be used to link the patient to a treatment arm and will specify a unique medication number for the first package of study drug to be dispensed to the patient. The randomization number will not be communicated to the caller.

The randomization numbers will be generated using the following procedure to ensure that treatment assignment is unbiased and concealed from patients/subjects and Investigator staff. A patient randomization list will be produced by the IRT provider using a validated system that automates the random assignment of patient numbers to randomization numbers. These randomization numbers are linked to the different treatment arms, which in turn are linked to medication numbers. A separate medication list will be produced by or under the responsibility of Novartis Drug Supply Management using a validated system that automates the random assignment of medication numbers to packs containing the investigational drug(s).

The randomization scheme for patients will be reviewed and approved by a member of the Randomization Group.

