#### 6.6 Other assessments

#### 6.6.1 Clinical outcome assessments (COAs)

#### 6.6.1.1 Clinician reported outcomes (ClinRO)

The impact of study drug on the patient's physical functional status will be assessed using the NYHA classification I-IV (older children: 6 to < 18 years old) or Ross HF classification I-IV (younger children: 1 month to < 6 years old). The NYHA and Ross functional class assessments are reliable instruments for rating HF patients' functionality (Criteria Committee NYHA 1994, Ross 1992, Packer 2001, Rosenthal 2004).

The NYHA functional class system is commonly used and is a clinically important system for staging the severity of HF (Spertus 2005). Similar to NYHA, the Ross classification system is a common system for grading the severity of HF in infants (Ross 1992). The most recent pediatric HF Guidelines from the International Society of Heart and Lung Transplant (ISHLT) mention both NYHA and Ross as Heart Failure Severity Classifications (Kirk 2014). A one class change in the NYHA or Ross functional class scale is considered to represent a clinically significant change (Ross 1992, Madsen 1994) based on the fact that the four stages in each classification differ considerably in severity.

Assessment of NYHA/Ross class will be conducted at screening visits for Part 1 (Visit 1) and Part 2 (Visit 301); randomization for Part 2 (Visit 401); end of study for Part 2 (Visit 416/499), and other visits as per Table 6-1 and Table 6-2.

For the duration of Part 2, the same PedsQL, NYHA and Ross instruments based on the age at randomization should be used.

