#### 9.4.2 Statistical model, hypothesis, and method of analysis

The primary endpoint comparing the distributions for patients receiving LCZ696 and patients receiving enalapril will be assessed using a stratified Wilcoxon rank-sum analysis (Kawaguchi 2011), stratifying by modified age group (Group 1: 6 to < 18 years; Group 2a: 2 to < 6 years; Group 3a: 1 month to < 2 years) and NYHA/Ross class group (Class I/II; Class III/IV). The overall significance level (Type 1 error) of 0.05 (2-sided) will be used. In addition, the proportion of patients falling into each of the 5 ordered categories of the primary endpoint will be presented by treatment group. These proportions will be provided both hierarchically (only worst category counted for each patient), as the endpoint is defined, and overall, not accounting for whether a patient also had a worse event. Full analysis set will be used for these analyses.

In addition, the number and percentage of patients in each category will be provided by treatment group for each age group, each modified age group, and for overall.

Due to unresolvable technical reasons in study drug supply, the unforeseen intercurrent events of the USM leading to study treatment discontinuations are not related to disease progression, are not related to the assigned study treatment, and do not reflect a real-world setting. The exposure to the study treatment and study follow-up are reasonably long. Therefore, the ontreatment approach is considered to be more appropriate for the handling of USM-impacted patients in the primary analysis, utilizing the relevant components of the global rank endpoint including Category 1 and Category 2 status at the time of treatment discontinuation.

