2.1 Data analysis general information

The final CSR analysis will be performed by Novartis. The same analysis method used in the global SAP will be used for the each of the specified endpoints in this SAP. SAS version 9.4 or later software will be used to perform all data analyses and to generate tables, figures and listings.

Since the study was designed for the global population and all below indicated subpopulations are subsets of the Asia/Pacific subset of the global population and are not pre-specified for the design, the analysis results from them must be cautiously interpreted and no results can be confirmatory.

The PK results in Chinese may be summarized and analyzed in a separate report.

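### The Cox model for time to first Category 1 or 2 event omits NYHA/Ross class group, a randomisation factor that the primary test keeps; if class is prognostic, the test is mildly conservative and some power is lost

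*Protocol*

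**What the plan says.** Protocol Section 5.3 sets the randomisation strata: "Patients will be stratified by age group (Age Groups 1, 2 and 3) and NYHA/Ross class group (Class I/II, Class III/IV) at randomization". Section 4 says the same. The primary test in Section 9.4.2 is a stratified Wilcoxon rank-sum analysis by modified age group "and NYHA/Ross class group (Class I/II; Class III/IV".

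Section 9.5.1 (Part 2) then specifies, for time to first Category 1 or 2 event, a Cox "proportional hazards model with treatment as fixed-effect factor stratified by modified age group". Treatment is the only factor and modified age group the only stratifier. The section does not explain why class group is dropped.

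The supplied SAP is a regional supplement. It refers its methods to another document: "The same analysis method used in the global SAP will be used for the each of the specified endpoints in this SAP". Its Cox tables point to the main RAP. Neither the global SAP nor the main RAP was supplied, so this point concerns the protocol text.

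**The concern.** When a factor is used to balance the arms and also predicts outcome, the treatment estimate varies less from trial to trial than an analysis ignoring the factor assumes. The model-based test then rejects too rarely under the null, and the hazard ratio that is not conditional on the factor lies slightly nearer 1. The result is lost power, not false positives.

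The protocol gives some reason to expect class to matter. Section 6.6.1.1 says the NYHA classification "is a clinically important system for staging the severity of HF". The Amendment 5 rationale requires Ross class II or higher in Age Group 2 and explains: "This is based on the lower event rate observed in Age Group 2 patients vs. Age Group 1 patients". That links class with event risk, but for class I against II, not for I/II against III/IV.

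This is the first-listed secondary efficacy objective and supplies the clinical-event support for the composite primary endpoint. Its power is low, so avoidable losses are unwelcome.

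**Working it through.** **The plan's own figure.** The protocol states no power for the Cox analysis, so the check starts from the primary endpoint. Table 9-2 gives a Mann-Whitney probability of 0.5705, hence odds of (1 - 0.5705)/0.5705 = 0.753, as Section 9.7 states. The tie-corrected Wilcoxon power at 177 per arm, two-sided 0.05, is 69.8%, matching the stated 70%. Table 9-2 is therefore read correctly.

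**What Table 9-2 implies for the Cox test.**
- Category 1 or 2 risk at 52 weeks: 13 + 19 = 32% on enalapril, 9 + 15 = 24% on LCZ696.
- Hazard ratio with exponential times: ln(0.76)/ln(0.68) = 0.712.
- Expected events: 180 × 0.32 + 180 × 0.24 = 100.8.
- Power by Schoenfeld's formula: Φ(|ln 0.712| × √100.8 / 2 - 1.96) = Φ(-0.25), about 40%. Reaching 80% would take 272 events.

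**Simulation of the omission.** From the documents: N = 360, 1:1 allocation, 52 weeks, 32% control risk, hazard ratio 0.712 within class. Assumed, because the documents do not give them: class III/IV share 15-50%, class hazard ratio 1.5-4, age mix 60/25/15%, blocks of 4, and two-sided 0.05 for this secondary test. One set of age groups served for both randomisation and analysis. Null runs used 28% risk in both arms. Each scenario had 20,000 trials, so the Monte Carlo SE is about 0.15 points for type I error and 0.35 points for power.

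| Class hazard ratio (assumed) | Type I error, age strata only | Power gain from adding class, N = 360 | Same, N = 375 | Hazard ratio without class |
|---|---|---|---|---|
| 1.5 | 4.6-4.9% | 0.2-0.5 points | 0.2-0.5 | 0.71 |
| 2 | 4.5-4.7% | about 1 | 1.0-1.4 | 0.71-0.72 |
| 3 | 3.8-4.1% | 3-4 | 2.7-4.2 | 0.72 |
| 4 | 3.5-3.8% | 5-6 | 5.0-6.4 | 0.72-0.73 |

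With class in the strata, type I error is 4.6-5.1% and the hazard ratio is 0.71. Across scenarios, power is 33-39% without class and 39-40% with it. The mean SE of the log hazard ratio is 0.201-0.203 either way, so the confidence interval does not narrow. The gain comes from the less attenuated estimate and a test nearer its nominal size. Age strata with class as a covariate do equally well: type I error 4.7-5.2%, power 39-40%. The N = 375 column reflects the number in the Amendment 7 rationale ("339 of 375 randomized patients who received study drug").

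**Second calibration.** Holding the overall risks at exactly 32% and 24%, power is 38-39% without class and 39-45% with it. The gains are 0.3-0.5, 0.7-1.5, 2.8-4.0 and 4.8-6.5 points at class hazard ratios 1.5, 2, 3 and 4.

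**Cross-check.** A separately coded simulation (class III/IV share 15% or 30%, same overall risks, null risk 32%) gave age-only type I error of 4.7-4.8%, 3.9-4.0% and 3.4-3.5% at class hazard ratios 2, 3 and 4. Power losses were about 1, 3-4 and 5-7 points. With no class effect, power was 39.6-39.9% without class and 39.7-39.9% with it, so the adjustment costs nothing.

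**The case against.** The strongest reply concerns weight, and much of it stands.

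- **The larger losses rest on assumption.** No document gives a class hazard ratio or a class III/IV share. With 32% control risk overall, a class hazard ratio of 4 implies 12-month control risks of 49-69% in class III/IV against 15-26% in class I/II, and nothing in the protocol supports so wide a gap. At 1.5 to 2 the loss is about 1 point or less. This stands.
- **The 33% low end depends on calibration.** It comes from fixing the hazard ratio within class at 0.712. With the overall risks held at Table 9-2, the planned model keeps 38-39%, close to the 40% benchmark, so the effect is better read as a gain forgone. This stands, though the gains are of similar size under both calibrations.
- **The shift in the hazard ratio is not bias in the usual sense.** The two models estimate different quantities, one conditional on class and one not. This stands.
- **Category 2 is not all hard outcome.** It includes worsening heart failure managed without hospitalisation. This stands, and the endpoint is better called clinical-event support.
- **The choice may be deliberate.** All three secondary efficacy models in Section 9.5.1 stratify by modified age group only, and six strata could be thin. But the other two models, for NYHA/Ross class and PGIS, adjust for their own baseline value, and the Cox model adjusts for nothing beyond age. Thin strata can be avoided by using a covariate.
- **The global SAP may already include class.** It may, which is a reason to check it, but the protocol text would still need to agree.

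None of these points gives a reason for leaving a randomisation factor out of the model.

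**Conclusion.** The point holds, as a minor one worth correcting. The Cox model drops a factor used in both randomisation and the primary test, without explanation. If class group is prognostic, the test is mildly conservative: the effect is negligible at a class hazard ratio of 1.5 to 2 and costs roughly 3 to 6 points of power at 3 to 4. The reported hazard ratio moves from 0.71 to at most 0.73. Type I error is not inflated and no conclusion would be invalid. The direction does not depend on the assumed class share or age mix; the size depends mainly on the class hazard ratio, which the documents do not give. Low power is a separate matter that this change would not cure, since power stays at about 39-45% with class included.

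**What to change.** In Section 9.5.1, stratify the Cox model by modified age group and NYHA/Ross class group, as in Section 9.4.2. If strata prove sparse in Group 3a, keep the age strata and enter class group as a covariate. Choose between the two forms on blinded stratum counts, before unblinding. If class is left out on purpose, state the reason in one sentence. Confirm that the global SAP says the same.

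The NYHA/Ross model needs no change. Adding class group to the PGIS model is optional, because it already adjusts for baseline PGIS.

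The cost is one line of protocol text and a check of the global SAP. The factor is already collected. The one drawback is small strata: with 15% of patients in Group 3a and 15% in class III/IV (both assumed), the smallest of six would hold 360 × 0.15 × 0.15, about 8 patients. The covariate form avoids this and performed the same in simulation.
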